The secondary objective (1) and (2) will be addressed using data collected from questionnaires completed by National Dental PBRN practitioners. As of June 2014, there are 2785 practitioners who reported performing nonimplant restorative procedures on the Enrollment Questionnaire. It is anticipated that approximately 1500 practitioners will complete the questionnaire. The primary measures to be calculated are percentages and confidence intervals (CIs) for prevalence of categories of response to the questionnaire items. Precision of estimation for these measures was calculated as the length of 95% CIs for a range of values of prevalence from 5% to 50%. CIs were based on the normal approximation to the binomial distribution. The maximum CI width occurs when prevalence equals 50%, with widths decreasing symmetrically on each side of this value.

Given the anticipated sample size of 1500 questionnaires, the expected total width of the 95% CI would be 5.06%, that is,  $\pm 2.53\%$ . Thus, for any value of prevalence, this sample size would provide sufficient precision to estimate the prevalence within no more than  $\pm 2.53\%$ , at the 95% confidence level. Smaller values of prevalence yield narrower expected CI widths, so that the expected CI widths for prevalence equal to 5% would be  $\pm 1.10\%$  and for prevalence equal to 10%, would be  $\pm 1.52\%$ .

The chart shows the total widths of expected 95% CIs for the proposed sample size of 1500 questionnaires, and for sample sizes of 1000, 2000, 2500 and 2785 questionnaires.

For the secondary objective (3) and (4), precision of estimation of the percentage of crowns rated as unacceptable by the laboratories will depend on the number of laboratories, number of crowns submitted to each laboratory, and the ICC for ratings within the same laboratory. Precision of estimation assumed 200 laboratories, each examining 20 crowns, 5% prevalence of suboptimal ratings, and ICC values of 0.0 to 0.05.

The chart presents half-widths of expected 95% CIs.

ICC	1/2 Width of 95% CI
0	0.68%
0.01	0.74%
0.02	0.79%
0.03	0.85%
0.04	0.90%
0.05	0.94%

The proposed sample size would provide estimation within  $\pm 0.68\%$  to  $\pm 0.94\%$  of a true 5% rate for this range of values of ICC.

Precision of estimation of agreement between ratings by the laboratories and the dentists will be driven by the level of agreement on crowns rated as unacceptable, since this is expected to be only 5% of the total sample. Assuming that 4000 crowns will be evaluated, approximately 200 are expected to be judged unacceptable. Ignoring the effect of clustering, if agreement between dentist and laboratory ratings is 90%, the expected 95% CI would be (85.8%, 94.2%), or estimation within  $\pm 4.16\%$ . For 80% agreement, the expected CI is (74.5%, 85.5%), or estimation

within  $\pm 5.54\%$ . If agreement is 70%, the expected CI is (63.6%,76.4%), or estimation within  $\pm 6.35\%$ .

### 11.3 Final Analysis Plan

**Primary objective:** (1) Estimate the percentage of single-unit crowns deemed acceptable by the practitioner at clinical try-in, and (2) identify factors associated with crown success.

The primary analysis for this aim will utilize generalized linear models to conduct logistic regression analysis, accounting for clustering of observations contributed by the same practitioner. A term representing the individual practitioner will be included as a random effect in the model. Estimation will be conducted using generalized estimating equations (GEE). The outcome variable will be dichotomous, indicating a crown being judged unacceptable by the practitioner.

Blocks of variables representing prosthodontic technique factors, patient/clinical factors and dentist factors will be evaluated as potential predictors of unacceptable crowns. These will be included as fixed effects in the model. Initial analysis will utilize separate models for each of the potential predictor variables. Multivariable models will be constructed using the variables found to be significant in each block and across blocks. These will be evaluated as predictive models for unacceptable crowns.

**Secondary objective:** (1) Quantify the prevalence of different methods and procedures utilized with crown preparations, and (2) explore whether these methods are significantly associated with dentist and practice characteristics.

The methods and procedures that will be included in the questionnaire are (1) crown preparation techniques; (2) impression techniques and impression materials; (3) materials used to fabricate crowns; (4) indications for recommending a single-unit crown restoration to a patient; and (5) the number of different dental laboratories to which the practitioners sends single-unit crowns to be fabricated.

Questionnaire results from approximately 1500 practitioners will be used to estimate frequencies of responses indicating each of the methods and procedures. Point estimates and 95% CIs for percentages of responses for each category will be calculated. The expected numbers of categories for each of the methods and procedures classifications are: three crown preparation techniques; three each impression techniques and impression materials, yielding nine combinations; five crown fabrication materials; and five indications for recommending a single-unit crown restoration to a patient. Additional categories may occur. If substantial numbers of a particular response occur, these will be counted as additional categories. Summary categories including less-commonly-occurring responses may be coded.

The number of different dental laboratories to which a practitioner sends single-unit crowns is expected to range from one to five. The median is expected to be three laboratories. Descriptive statistics will be calculated including the mean and median and corresponding 95% CIs.

Frequencies and percentages of the total responses will be calculated for each category, and 95% CIs will be calculated. A Bonferroni-type adjustment will be applied in order to obtain simultaneous coverage of approximately 95% for all categories of the classification variables.

The associations between use of specific methods and dentist- and practice-level characteristics will be evaluated using contingency tables and multiple logistic regression analysis. Unadjusted odds ratios and chi-squared statistics will be calculated from contingency tables. Logistic regression models including multiple characteristics and adjusting for region will be used to calculate adjusted odds ratios for each of the characteristics.

All valid questionnaire data obtained from the practitioner questionnaire will be utilized in the analyses. Since this is a cross-sectional questionnaire, loss to follow-up is not a consideration. No imputation of missing values will be conducted.

**Secondary objective:** (3) Estimate the percentage of single-unit crown preparations, impressions, and opposing casts that are deemed optimal by the dental laboratory, and (4) examine if this laboratory rating is associated with practitioner acceptability.

This aim will be addressed by calculating the percentage of crowns judged sub-optimal by the dental laboratories. A 95% CI for this percentage will be calculated.

Association with practitioner judgment of acceptability of the crown will be evaluated by including the laboratory rating as a predictor variable in the logistic regression model developed in Primary Objective (1). This will provide an adjusted odds ratio for the laboratory rating, accounting for the other predictive characteristics included in the model. Clustering by practitioner and by laboratory will be accounted for in this model. If the level of agreement between the practitioner and the laboratory is very high, this approach might not be feasible, as the estimation algorithm for the logistic model would be unstable, and would be likely to fail due to lack of convergence. If this occurs, agreement between laboratory and dentist ratings will be calculated separately using Cohen's kappa for each practitioner and a weighted average will be calculated using the number of crown assessments per dentist, in order to obtain a summary measure of agreement.

---

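### The Stage 1 precision of ±2.53% holds for single unadjusted 95% intervals, but the Bonferroni-adjusted intervals planned for the same percentages are 22% to 41% wider within a classification

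*Protocol*

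**What the plan says.** Section 11.2 of the protocol justifies the Stage 1 questionnaire by the width of confidence intervals. The method is given as "Precision of estimation for these measures was calculated as the length of 95% CIs for a range of values of prevalence from 5% to 50" per cent, and "CIs were based on the normal approximation to the binomial distribution". The result is "Given the anticipated sample size of 1500 questionnaires, the expected total width of the 95% CI would be 5.06" per cent in total, or ±2.53%. The section then generalises: "Thus, for any value of prevalence, this sample size would provide sufficient precision to estimate the prevalence within no more than" ±2.53%, at the 95% level, with ±1.10% at 5% prevalence and ±1.52% at 10%. The same text appears twice in the section, once under the primary objective and once under secondary objectives (1) and (2).

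Section 11.3 sets out the analysis of the same questionnaire percentages. It lists the expected categories: "three crown preparation techniques; three each impression techniques and impression materials, yielding nine combinations; five crown fabrication materials; and five indications for recommending" a crown. It warns that "Additional categories may occur". It plans 95% intervals for the category percentages and then states: "A Bonferroni-type adjustment will be applied in order to obtain simultaneous coverage of approximately 95% for all categories of the classification variables".

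**The concern.** The interval that supports the sample size is not the interval that section 11.3 plans to report. Section 11.2 treats each percentage alone at 95%. Section 11.3 asks for about 95% coverage over a set of percentages together, which needs a larger multiplier for each one. Section 11.2 neither mentions nor allows for that.

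Secondary objective (1) is an estimation aim, and interval width is its only sample-size justification. Someone comparing the reported adjusted intervals with section 11.2 would find the stated precision missed, with nothing in the protocol to explain the gap.

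**Working it through.** **Inputs.** n = 1,500, the normal-approximation interval, and prevalences of 50%, 10% and 5% (section 11.2). Category counts k = 3 (preparation techniques), 9 (impression combinations), 5 (materials) and 5 (indications), which sum to 22 (section 11.3). No finite population correction is applied, because section 11.2 applies none. Section 11.2 takes 50% as the worst case: "The maximum CI width occurs when prevalence equals 50%, with widths decreasing symmetrically on each side of this value".

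**Step 1: reproduce the stated figures.** Half-width = z × √(p(1−p)/n) with z = 1.96:

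- p = 0.50: 1.96 × √(0.25/1500) = 2.53%
- p = 0.10: 1.96 × √(0.09/1500) = 1.52%
- p = 0.05: 1.96 × √(0.0475/1500) = 1.10%

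All three match section 11.2, so its figures are single, unadjusted 95% intervals.

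**Step 2: apply the Bonferroni adjustment.** Replace 1.96 by the normal quantile at 1 − 0.025/k. The widening ratio z/1.96 does not depend on prevalence.

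| k | z | Ratio to 1.96 | p = 50% | p = 10% | p = 5% |
|---|---|---|---|---|---|
| 1 (as stated) | 1.960 | 1.00 | ±2.53% | ±1.52% | ±1.10% |
| 3 | 2.394 | 1.22 | ±3.09% | ±1.85% | ±1.35% |
| 5 | 2.576 | 1.31 | ±3.33% | ±2.00% | ±1.45% |
| 9 | 2.773 | 1.41 | ±3.58% | ±2.15% | ±1.56% |
| 22 (one family) | 3.052 | 1.56 | ±3.94% | ±2.36% | ±1.72% |

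A Šidák adjustment gives almost the same ratios: 1.22, 1.31, 1.41 and 1.55.

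**Step 3: find where the 2.53% ceiling fails.** The adjusted half-width stays within 2.53% when p(1−p) ≤ 1500 × (0.0253/z)². For k = 3 the right-hand side is 1500 × (0.0253/2.394)² = 0.1675, and solving gives p ≤ 21% or p ≥ 79%. In the same way:

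- k = 3: exceeded between about 21% and 79%
- k = 5: exceeded between about 18% and 82%
- k = 9: exceeded between about 15% and 85%

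As an illustration, suppose the categories of a classification are mutually exclusive and equally common. Three at 33% each give ±2.91%, and five at 20% each give ±2.66%, both above the ceiling. Nine at 11% each give ±2.25%, which is within it.

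**The case against.** **No figure in section 11.2 is miscalculated.** This stands. Planning for one percentage and also reporting simultaneous intervals is not contradictory in itself. The fault is that section 11.2 does not say which interval its figure describes, while section 11.3 plans a different one.

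**A reader might infer that the precision claim fails for every multi-category item.** The documents do not support that. The claim is a ceiling, and Step 3 shows that it still holds at low and high prevalences. What fails is the ceiling in mid-range, and the specific ±1.52% and ±1.10%.

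**A reader might take 56% as the size of the problem.** That needs one family of all 22 categories. Section 11.3 lists the categories by classification and does not say whether the adjustment runs within each classification or across all of them. Within a classification the range is 22% to 41%.

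**A reader might infer that 1,500 is too few, or that the target cannot be reached.** Without a finite population correction, keeping ±2.53% at 50% prevalence needs about 2,239 (k = 3), 2,592 (k = 5) or 3,004 (k = 9) respondents, which invites comparison with the 2,785 eligible practitioners. But that comparison brings in a finite population that the calculation ignores. If inference were to those 2,785 (an assumption), the correction factor is √((2785 − 1500)/2784) = 0.68. The adjusted worst-case half-widths become ±2.10%, ±2.26% and ±2.43% (±2.68% for k = 22). The numbers needed fall to 2239/(1 + 2238/2785) ≈ 1,241 for k = 3 and 3004/(1 + 3003/2785) ≈ 1,445 for k = 9. If inference is to a wider population, 2,785 is only a recruitment limit. Either way, infeasibility is not shown. The correction does not remove the mismatch, because it shrinks adjusted and unadjusted intervals alike and the stated figures were computed without it.

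**Unadjusted intervals may also be reported.** Section 11.3 mentions 95% intervals for each category before it introduces the adjustment. This is a fair point, but the section does not say that both sets will be shown or which is the headline.

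**The consequence is small.** This is also fair. The outcome is descriptive, 1,500 is an anticipated return and not a number derived from a target, and no precision threshold is set that ±3.1% to ±3.6% would fail.

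**Conclusion.** The point holds as a mismatch between sections 11.2 and 11.3. The figures ±2.53%, ±1.52% and ±1.10% describe single unadjusted 95% intervals. The adjusted intervals planned for the same percentages are wider by 22%, 31% and 41% for 3, 5 and 9 categories, so the worst-case half-width within a classification is ±3.09% to ±3.58%. These sizes rest on n = 1,500, the normal approximation, the expected category counts, Bonferroni within each classification and no finite population correction. Further categories would widen the intervals more. The effect is confined to the stated precision of Stage 1 estimates. It gives no reason to doubt the sample size, and it affects no hypothesis test.

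**What to change.** Choose one of two wordings for section 11.2, and use it in both places where the text appears.

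1. Restate the precision for the adjusted intervals: at most about ±3.1% to ±3.6% within a classification, with the 10% and 5% figures taken from the table above. Name the Bonferroni family. If the family is all 22 categories, the maximum is ±3.94%.
2. Keep ±2.53%, ±1.52% and ±1.10%, and state that they refer to unadjusted per-category 95% intervals. In section 11.3, make those the headline intervals, give the adjusted ones as a supplement, and name the family.

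Neither option changes the sample size or the data collected. The cost is a few sentences and, under the first option, a slightly less favourable precision statement.

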## 4 STUDY DESIGN

### Stage 1: Questionnaire of approximately 1,500 practitioners.

To be eligible for Stage 1, practitioners must be enrolled in the National Dental PBRN, complete an Enrollment Questionnaire, and report on the enrollment questionnaire that they routinely perform restorative dentistry in their practices.

This practitioner questionnaire component of the study (Stage 1) is a cross-sectional study that is limited to network practitioners who report doing at least some single-unit fixed prosthodontic treatment. A random selection of 2,300 practitioners will be invited to complete an online or printed questionnaire, among all of the estimated 2,785 practitioners who meet inclusion criteria. This questionnaire portion of the study will query use of specific prosthodontics techniques (impression techniques; impression materials; use of digital impressions; materials used for prosthetic crowns, crown preparation techniques; techniques and materials used for hemostasis during impressions; techniques and materials used for bite registration for single-unit crowns; dental cements used for single-unit crowns); clinical scenarios used to describe indications for recommending a single-unit crown restoration to a patient; and the number of different dental laboratories to which the practitioner sends single-unit crowns to be fabricated. Dentists will be informed that the questionnaire may be completed either electronically or on paper.

Development and administration of the questionnaire is detailed in Section 7.1.

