## 5.3 Strategies for Recruitment and Retention

### 5.3.1 Stage 1 (Questionnaire Component)

Eligible dentists for the Stage 1 questionnaire will be identified based on the criteria noted from their responses on the Enrollment Questionnaire. All eligible dentists will first receive a study invitation email from the CC on behalf of the RC inviting them to participate in the study. The invitation will include a link to the electronic version of the questionnaire. Dentists will have an opportunity to complete an electronic or paper version of the questionnaire in order to increase participation rates. Based on previous regional PBRN questionnaire studies, we anticipate a response rate of approximately 60-70%. Calls will be held as needed with the RCs to review contact information for eligible dentists, discuss recruitment issues and enrollment progress, manage study documentation and procedures, and troubleshoot problems related to enrollment.

Dentists will be reimbursed \$75 for participation in the Stage 1 study. This is a cross-sectional questionnaire study; retention strategies are not applicable.

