### Questionnaire Content

The questionnaire includes items to collect the date and assess the outcome measures specified in subsection 3.2. Some information will be collected from the National Dental PBRN Enrollment Questionnaire (e.g., demographics and practice characteristics) and linked to participants' responses to the study questionnaire.

Each practitioner's "clinical acceptability" level will be ranked using a vignette series within the questionnaire. Practitioners will be shown a series of clinical photographs and scenarios of crowns and impressions and asked to rate these as clinically acceptable or unacceptable. As an example, practitioners will be shown a picture of an impression with a small bleb or defect at the finish line, and asked if it is clinically acceptable. These rankings of practitioner exactness will help us interpret the results of the study.

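### Stage 1 prevalences are unweighted percentages of returned questionnaires with 30-40% non-response expected; the ±2.53% precision is sampling error only and no respondent/non-respondent comparison is planned

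*Protocol*

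**What the plan says.** Section 4 (Stage 1) describes the sample: "A random selection of 2,300 practitioners will be invited to complete an online or printed questionnaire", drawn "among all of the estimated 2,785 practitioners who meet inclusion criteria". Section 5.3.1 gives the expected return: "we anticipate a response rate of approximately 60-70" percent. Section 11.2 adds: "It is anticipated that approximately 1500 practitioners will complete the questionnaire".

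On precision, section 11.2 states: "Given the anticipated sample size of 1500 questionnaires, the expected total width of the 95% CI would be 5.06" percent. It puts the margin at ±2.53% with 95% confidence and claims: "for any value of prevalence, this sample size would provide sufficient precision to estimate the prevalence within no more than" that margin. It also gives ±1.10% at 5% prevalence and ±1.52% at 10%.

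On analysis, section 11.3 takes frequencies and percentages of the total responses, each with a 95% interval and a Bonferroni-type adjustment across categories. The analysis set is defined by "All valid questionnaire data obtained from the practitioner questionnaire will be utilized in the analyses". The same paragraph notes that a cross-sectional questionnaire has no loss to follow-up and that missing values will not be imputed. Unit non-response is not mentioned in section 11.

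On auxiliary data, section 5.1.1 makes a completed Enrollment Questionnaire an inclusion criterion for Stage 1. Section 7.1 (Questionnaire Content) says: "Some information will be collected from the National Dental PBRN Enrollment Questionnaire (e.g., demographics and practice characteristics"), to be linked to participants' answers. Section 3.2.1 names the enrollment questionnaire as the source of practitioner factors, which include years in practice and network region.

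On participation, section 11.1 compares dentists who take part in the first phase only with those who go on to the second. Both groups answered the Stage 1 questionnaire.

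**The concern.** The prevalence of methods and procedures is a secondary objective (section 3.1.2). Random invitation protects against selection at the invitation step, not at the response step. Dentists choose whether to answer, and section 7.1 assumes that those who never answer are not interested.

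If response depends on characteristics that also relate to the methods used, the respondent percentages are shifted and the intervals are centred in the wrong place. One of those two links is the protocol's own hypothesis: section 11.1 proposes that methods vary with dentist and practice characteristics. The other link, between those characteristics and response, could be examined with enrollment data, but no such check is written. The comparison in section 11.1 serves a different purpose and cannot show who failed to answer Stage 1. A reader of the published prevalences would see a narrow interval with nothing to say how far respondents resemble the network.

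**Working it through.** **Inputs from the protocol.** Invited 2,300 (section 4). Respondents about 1,500 (section 11.2). Response 60-70% (section 5.3.1). Stated half-width ±2.53% (section 11.2). Implied response 1,500/2,300 = 65.2%, so non-response is 34.8%.

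**Input that is an assumption.** The difference *d* between prevalence in respondents and in non-respondents. The documents give no value; 2 to 20 points is shown.

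**Step 1: reproduce the plan's figures.** Half-width = 1.96 × √(p(1−p)/n), with n = 1,500:
- p = 50%: 1.96 × √(0.25/1500) = 2.53 points, total width 5.06
- p = 10%: 1.96 × √(0.09/1500) = 1.52 points
- p = 5%: 1.96 × √(0.0475/1500) = 1.10 points

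All three match section 11.2.

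**Step 2: bias of the respondent-only percentage.** Bias = (1 − response rate) × d. At 65.2% response (factor 0.348):

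| Assumed d (points) | Bias (points) |
|---|---|
| 2 | 0.70 |
| 5 | 1.74 |
| 10 | 3.48 |
| 15 | 5.22 |
| 20 | 6.96 |

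At 60% and 70% response, d = 5 gives 0.40 × 5 = 2.0 and 0.30 × 5 = 1.5 points; d = 10 gives 4.0 and 3.0.

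**Step 3: break-even difference.** Setting the bias equal to 2.53 points gives d = 2.53/(1 − response rate):
- 60%: 2.53/0.40 = 6.3 points
- 65.2%: 2.53/0.348 = 7.3 points
- 70%: 2.53/0.30 = 8.4 points

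For the narrower intervals at 65.2% response, the break-even is 1.10/0.348 = 3.2 points at 5% prevalence and 1.52/0.348 = 4.4 points at 10%. At such low prevalences these are large relative differences.

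**Step 4: coverage of a single nominal 95% interval.** Near 50% prevalence the standard error is √(0.25/1500) = 1.29 points. Coverage = Φ(1.96 − bias/SE) − Φ(−1.96 − bias/SE).
- d = 5: bias/SE = 1.74/1.29 = 1.35; coverage about 73%
- d = 10: bias/SE = 3.48/1.29 = 2.69; coverage about 23%

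**Step 5: effect of the Bonferroni adjustment.** The simultaneous intervals in section 11.3 are wider. At 50% prevalence the half-width is 3.09 points for three categories, 3.33 for five and 3.58 for nine. The break-even against these is 3.09/0.348 = 8.9, 3.33/0.348 = 9.6 and 3.58/0.348 = 10.3 points. The comparison with 2.53 concerns the precision stated in 11.2, not every interval that will be reported.

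**The case against.** The strongest objection is that non-response weighting is detail often left to a statistical analysis plan, and none is at hand. It has some force: nothing in section 11.3 forbids weights. But the protocol is not merely silent. It defines the estimator as a percentage of returned responses, and it plans a participation comparison that cannot inform Stage 1 non-response.

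Second, the ±2.53% is described as a confidence-interval width at the 95% level, in a sample-size section where such figures normally exclude bias. That stands. A reader might infer that the figure is wrong; it is not, and the change needed in 11.2 is a clarification.

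Third, a reader might take the sentences on loss to follow-up and on imputation as dismissing non-response. They do not. A single questionnaire has no follow-up to lose, and the imputation sentence most naturally concerns unanswered items, since section 2.3.1 lets dentists skip questions. Neither sentence is an error.

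Fourth, the size of the bias rests wholly on assumed differences. That stands too: the documents do not support saying that the bias exceeds 2.53 points in fact.

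Fifth, the protocol works to limit non-response through reimbursement and paper and electronic modes (5.3.1), reminders (7.1), coordinator follow-up (10) and two-weekly reports by characteristics or region (15.4). These may reduce non-response or show who has answered so far, but none is a planned comparison with non-respondents or an adjustment. The adjustment for region in 11.3 applies to the association models, not to the prevalences.

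Last, a completed Enrollment Questionnaire does not guarantee that every item is filled in, and section 3.2.2 does not say which characteristics come from which questionnaire. The choice of weighting variables must respect that.

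**Conclusion.** The point holds as a low-cost improvement to a secondary objective, not as a wrong figure. The Stage 1 prevalences are unweighted respondent percentages with about 35% non-response expected, and nothing planned would show whether respondents differ from the rest. The stated precision is correct for sampling error and does not cover this source of error.

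Whether the bias matters depends on an unknown: it passes 2.53 points only beyond a difference of roughly 6 to 8 points over the anticipated response range, and a 5-point difference stays below it. The primary Stage 2 estimate of crown acceptability is outside this point.

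**What to change.** In section 11.3:
- Report the response rate, and compare respondents with non-respondents on Enrollment Questionnaire variables confirmed complete for all invitees, for example region and years in practice.
- Beside each unweighted prevalence, report one weighted by the inverse of the response proportion in cells of those variables, as a sensitivity analysis.

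In section 11.2, state that ±2.53% is sampling error only and excludes non-response bias. The paragraph appears twice there, under the primary and the secondary objective, so both places need the sentence.

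**Cost.** No new data collection if the enrollment items are complete. Weighted intervals are slightly wider: with an assumed weighting design effect of 1.1, 2.53 × √1.1 = 2.65 points. Weighting removes only the bias explained by the variables used, so similar weighted and unweighted results would be reassuring but not proof of no bias.
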